 - c) greater improvement or lesser impairment of quality of life after reconstruction of floor of lesser pelvis
2. To study if the different rehabilitation programmes used reflect differences in outcome measures in subgroup analyzes for both methods of reconstruction
3. To compare the health economic costs with the two techniques and to perform a cost-utility analysis (QALYs gained). The health economic analysis is optional to participating centres. Costs and health economics will be calculated only in centres that have routine registration (in electronic databases) of operation time, time at ICU, days in hospital, connected reoperations, connected readmissions and outpatient visits related to the index operation.

Investigational plan

Endpoints of study

1. Primary endpoint: Performance in Timed-stands test (TST)[9, 10]reflecting physical performance at 6 months from operation.
2. Secondary endpoints:
 1. Change in physical performance (3 months, 6 months and 1 year compared to preoperative)
 2. Primary wound healing assessed with the Southampton Wound Assessment Scale (SWAS)[11] at 3 months from operation
 3. Complications according to classification by Dindo-Clavien[12] (3 months, 6 months and 1 year)
 4. Proportion of persistent perineal sinus or fistula (3 months, 6 months, 1 year)
 5. Ability to sit (3 months, 6 months, 1 year)
 6. Change of pain and discomfort in gluteal region measured with VAS (3 months, 6 months and 1 year compared to preoperative)
 7. Change of quality of life measured with EQ-5D and EORTC forms C30 and CR29 (3 months, 6 months and 1 year compared to preoperative)
 8. Quality of life spot measures at 3 months, 6 months and 1 year

9. Length of hospital stay, costs of surgical treatments and QALYs gained at one year
10. Local recurrence during study period

Hypotheses of study

Primary hypothesis:

1. The reconstruction of lesser pelvis floor with APCI will result in better physical performance in operated patients compared to patients operated on with GMF.

Secondary hypotheses:

1. The assumed decrease of physical performance after the APCI operation will be less than after the GMF operation.
2. The reconstruction of lesser pelvis floor with APCI will result in better wound healing and less wound complications than the GMF operation.
3. The reconstruction of lesser pelvis floor with APCI will result in better ability to sit and lesser pain and discomfort in the gluteal region than the GMF operation,

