The participants are examined by a physiotherapist or a study nurse who is familiar with the protocol. Examinations of physical performance, wound healing and registration of quality of life and background information takes place:

1. within one week before the start of radiotherapy (or operation if examination before RT can not be accomplished) (wound healing excluded)
2. three months after the operation
3. six months after the operation
4. one year after the operation
5. at one late time point 2-5 years after the operation if previous analyses indicates a need for long time follow-up. The long time follow-up is optional for participating centres and will be decided later.

A separate detailed protocol of standardized examination procedures will be available for the physiotherapists and nurses involved in the study. A pre-study meeting for standardization of examinations will be arranged for participating centres.

The standardisation of operations will be secured with site visits from (or to) Stockholm Karolinska Sjukhuset Solna where the standard for GMF and APCI operations is defined.

The enrolment of a patient in the study is finalized with the randomization procedure on Internet. The web application at www.norrlandskirurgi.se is used for randomization.

The randomization is computed in blocks and stratified by:

- Centre
- Mode of preoperative radiotherapy (RT)
 - Short preoperative RT, (5 x 5 GY), **operation within one week from last RT dose**
 - Short preoperative RT, (5 x 5 GY) or long preoperative RT (25 x 1,8/2 GY), **operation 4 - 8 weeks from last RT dose**
 - Earlier RT for organs in the lesser pelvis in connection to a previous therapy but no additional RT before the current operation or other RT dose or timing of operation

The stratification and block randomization ensures that all above defined subgroups of patients will contain patients allocated evenly (or close to evenly) to both study arms. The size of the randomisation blocks will vary within predefined limits and the size of the block under use will be chosen by random from the alternatives given of limits.

Flowchart of NEAPE study

Surgeon and study nurse

MDT conference

- Identify APE and EAPE candidate patients =eligible rectal cancer patients
- Study nurse enter identified patients in register at www.norrlandskirurgi.se

Study nurse

For EAPE candidates, send invitation for preoperative visit to surgeon and physiotherapist or study nurse

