Blinding in surgical studies is hard to accomplish. This study is performed without attempts for blinding and thus the attending surgeon, the examiner of physical performance and the patient do not have to be blinded.

Concomitant therapy

Pre- and postoperative radiotherapy or chemo radiotherapy can be utilised according to multidisciplinary team decisions at each centre.

Postoperative rehabilitation programmes

Due to already existing routines, we consider it not realistic to prescribe only one uniform programme. Instead, the patients will be allocated to either an established programme[7] or to an accelerated programme that has been used in another centre. Both rehabilitation programmes are standardized, written and should be followed explicitly. The descriptions of both programmes can be downloaded from the study webpage at www.norrlandskirurgi.se.

Participating centres must choose one of the rehabilitation programmes and use that program for all their study patients. The rehabilitation programmes at hand are studied earlier and considered safe [21].

Evaluation of outcome measures and safety

Measures of physical performance

The study physiotherapist or nurse will examine measures of physical performance.

A "timed-stands test" is to be performed by recording the time needed to stand ten times from a standard chair[9, 10]. The test gives a measure of lower extremity muscle strength, muscle coordination and tenderness of the gluteal region (caution when sitting) and gives the possibility to correlate the results to a reference population studied earlier[9]. The test is validated.

A complementary step test is performed at some participating centres (optional test)[22].

The study physiotherapist or nurse will process measures of quality of life, pain, discomfort and ability to sit. Data will be registered on forms (see Appendix) or directly in the electronic database.

Quality of life is measured with the global instrument EQ-5D and the cancer specific instrument EORTC QLQ-C30 and QLQ-CR29. The forms will be sent to the patient prior to the follow-up visits and the study physiotherapist or nurse who cares for the data to be registered in the study database will collect the completed forms. Completeness of data should be checked during the visit so that any incomplete data can be corrected together with the patient.

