1. Costs of surgical treatments and QALYs gained are calculated for a subpopulation of the study population. Registration of parameters needed for the health economic calculations is optional for the participating centres and the subpopulation will be included only from centres that collect health economic data in their computer systems. Costs of surgical treatments including surgical complications up till 12 months will be calculated according to health economic standards and QALYs gained will be compared between study arms.
2. Two different rehabilitation programmes will be used for study patients and every participating centre must decide which of the programmes to use. The centre must stay to the chosen rehabilitation programme throughout the study. A subgroup analysis will be performed with the aim to reveal if the rehabilitation program has an impact on the main and secondary outcomes.

Safety analyses

An independent observer will be appointed with the task to contact each centre yearly and ask for unforeseen adverse events and problems. If severe adverse events occur the PI and the independent observer have the responsibility to decide whether the study can continue or should be stopped.

All safety analyses comparing the treatment groups will be performed based on the intent-to-treat population. All statistical tests of safety will be conducted at a two-sided alpha-level of 0.05. The safety analysis variables include, but are not restricted to:

- Postoperative mortality in 30 days
- Postoperative complications Grade IIIb or higher according to Dindo-Clavien
- Proportions of serious adverse events

Interim analyses

Interim analyses will be performed only if the study inclusion period exceeds 5 years. Safety analyses are exceptions that are performed whenever proposed by the independent observer.

Informed consent, ethical review and regulatory considerations

Informed consent

The informed consent document with study information will be used to explain in simple terms to patients what participation in the study means for the patient. The patient will get information of the risks, benefits and the alternatives available.

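### The stated aim of revealing the impact of the rehabilitation programme cannot be met, because programme is chosen by centre, nested in centre and not randomised

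*Protocol*

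**What the plan says.** The aim appears twice. Secondary objective 2 of the protocol reads: "To study if the different rehabilitation programmes used reflect differences in outcome measures in subgroup analyzes for both methods of reconstruction". The section Subgroup analyses, item 2, puts it more strongly: "A subgroup analysis will be performed with the aim to reveal if the rehabilitation program has an impact on the main and secondary outcomes".

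How a patient comes to follow a programme is set out under Postoperative rehabilitation programmes. The reason for having two is local practice: "Due to already existing routines, we consider it not realistic to prescribe only one uniform programme". The rule is: "Participating centres must choose one of the rehabilitation programmes and use that program for all their study patients". Subgroup analyses repeats that "every participating centre must decide which of the programmes to use" and adds: "The centre must stay to the chosen rehabilitation programme throughout the study". The section Preoperative measures likewise requires one programme for the whole study.

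One sentence could be misread: "Instead, the patients will be allocated to either an established programme[7] or to an accelerated programme that has been used in another centre". The paragraph after it leaves the choice to the centre.

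Randomisation, in Summary of study design, concerns the reconstruction method only. "The randomization is computed in blocks and stratified by" introduces two factors, centre and mode of preoperative radiotherapy. Nowhere does the protocol say that the programme comparison is non-randomised, nested in centre or exploratory.

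**The concern.** The aim is worded as a question of cause: does the programme change the main and secondary outcomes? To answer it, patients who are otherwise comparable would have to follow different programmes. Here all patients of a centre follow the same one, and the centre chose it because of how it already worked.

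Centres differ in other ways that can move the outcomes. Enhanced-recovery routines are chosen by the clinic and then held fixed (Preoperative measures). Radiotherapy and chemotherapy follow local team decisions (Concomitant therapy). Removal of the coccyx and omentoplasty are optional. The Timed-stands test is run by local examiners without blinding (Blinding).

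At stake is a named secondary objective. Followed as worded, it would lead the trial to credit a programme with differences that may belong to the centres using it, across the primary and all secondary outcomes.

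**Working it through.** **1. The protocol's own figure.** It gives none for the programme analysis. Its sample size for APCI versus GMF (section Sample size) uses 63% and 30% low performers, alpha 0.05 (taken as two-sided), and 20% loss. With the unpooled formula n = (z_alpha + z_power)² × [p1(1−p1) + p2(1−p2)] / (p1−p2)²:

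- 90% power: (1.960 + 1.282)² × (0.2331 + 0.2100) / 0.1089 gives 43 per arm; 43/0.8 gives 54, total 108. This matches.
- 80% power: 32 per arm; 32/0.8 = 40, total 80. This matches the fallback.

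Evaluable patients: 108 × 0.8 = 86.4, taken as 86.

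**2. Can programme be separated from centre?** The number of centres K is not stated. Use indicators for K centres, plus arm, plus programme, with programme constant within centre. The programme column is then the sum of the indicators of the centres that use it. Ranks were computed for K = 2, 4, 6, 8, 12 and 18. The last is 108/6, from the required capacity of at least 6 patients per centre.

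- Centre + arm: rank K+1 (7 for K = 6).
- Adding programme: still K+1 (7), in every case. With centre in the model as fixed effects, the programme effect is not estimable.
- Adding arm-by-programme to centre + arm: K+2 (8).
- Letting the arm effect differ by centre: 2K (12). Adding arm-by-programme to that: still 2K (12).

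The last line matters for the remedy. A difference between programmes in the APCI-versus-GMF effect is also a contrast between centres. What randomisation protects is the arm effect inside each programme, because arms are balanced within each centre.

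**3. How much information is left?** Without fixed centre effects, the programme contrast compares centres and has about K−2 error degrees of freedom: 0 for two centres, 2 for four, 4 for six, 10 for twelve. The authorship rule under Final report signature provides for the case of five centres or fewer, so a small K is within what the protocol foresees.

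**4. If centre were ignored altogether.** This is conditional, since the protocol names no model. Assume equal centres of m = 86/K patients and a between-centre intracluster correlation (ICC) from 0.01 to 0.10; neither K nor the ICC is in the protocol. Design effect DE = 1 + (m−1) × ICC. True two-sided error of a nominal 5% test = 2 × [1 − Φ(1.96/√DE)], by normal approximation.

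| Centres | m | ICC 0.01 | ICC 0.02 | ICC 0.05 | ICC 0.10 |
|---|---|---|---|---|---|
| 2 | 43.0 | 0.100 | 0.148 | 0.266 | 0.390 |
| 4 | 21.5 | 0.074 | 0.099 | 0.168 | 0.262 |
| 6 | 14.3 | 0.066 | 0.082 | 0.129 | 0.199 |
| 8 | 10.8 | 0.061 | 0.073 | 0.108 | 0.163 |
| 12 | 7.2 | 0.057 | 0.064 | 0.087 | 0.123 |

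Example, two centres at ICC 0.10: DE = 1 + 42 × 0.10 = 5.2, and 1.96/√5.2 = 0.86, so the error is 0.39. The table counts clustering only. Bias from systematic differences between the two groups of centres comes on top, and more patients per centre would not reduce it.

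**The case against.** The strongest reply is that the protocol writes no model. A reader might infer a patient-level test that ignores centre, with standard errors that are too small. The text does not say that, and how centre enters the analysis may properly be left to a statistical analysis plan. This stands: the error rates above are conditional and are not a fault of the protocol. It does not rescue the aim, because the confounding is fixed by the design and no model removes it.

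A reader might also infer that programme and centre are completely confounded, so that nothing can be estimated. That goes too far. With several centres per programme, a random-centre model gives an estimate, though a non-randomised one on few degrees of freedom. Referred patients may also finish rehabilitation at another hospital (Summary of study design), so the link to the operating centre need not be perfect; the programme is still set by hospital and not by chance.

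A third inference would be that a test of arm by programme is safe because arms are randomised within centre. Step 2 shows otherwise.

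Other mitigating points are fair. The choice by centre is openly stated. Objective 2 speaks of outcome differences within both reconstruction methods, which is softer than the wording under Subgroup analyses. Radiotherapy mode is a stratification factor, examinations follow a common manual with a pre-study meeting, and operations are standardised by site visits. These narrow the differences between centres but do not make the programme comparison randomised.

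**Conclusion.** The point holds as a fault in the stated aim. Programme is chosen by centre, from existing routine, and is nested in centre. The trial therefore cannot reveal the impact of the programme; it can only describe how groups of centres differ. This rests on the protocol's own rules and needs no assumed figure.

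The size of any false-positive excess is uncertain. It is about 6% to 39% instead of 5% over 2 to 12 assumed centres and ICC 0.01 to 0.10, and only if centre is left out of the analysis.

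The damage is limited. The primary comparison of APCI with GMF is not touched, nor is that comparison within each programme. No sample size or success rule depends on the programme analysis. It should be corrected because it is a named secondary objective with causal wording and no stated limitation.

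**What to change.** 1. Reword secondary objective 2 and item 2 of Subgroup analyses without causal language, and state there that programme is chosen by centre, nested in centre and not randomised.
2. Under Postoperative rehabilitation programmes, replace the wording on allocation so that it does not suggest assignment of individual patients.
3. Make the main subgroup result the APCI-versus-GMF difference within each programme, which is a valid randomised comparison because randomisation is stratified by centre.
4. Label any difference of that effect between programmes as exploratory, since it too is a contrast between centres, and allow for centre in its standard error.
5. Report outcome levels by programme descriptively only, with the number of centres behind each.

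The cost is a few sentences and a modest change to the analysis. No data collection or sample size changes. The downside is that the trial gives up a claim about programme effect, which it could not have supported.

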Appendix

Form S1: Surgeon, first postoperative visit, workup and TNM

(same as Swedish CRC register at www.incanet.se, paper form or www.norrlandskirurgi.se outside Sweden)

SEPARATE DOWNLOAD

Form S2: Surgeon, early complications within 30 d

(same as Swedish CRC register at www.incanet.se, paper form or www.norrlandskirurgi.se outside Sweden)

SEPARATE DOWNLOAD

Form S3: Surgeon, all postoperative visits

SEPARATE DOWNLOAD

Form S4: Surgeon, late complications, postoperative visits later than 30 days

(same as Swedish CRC register at www.incanet.se, paper form or www.norrlandskirurgi.se outside Sweden)

SEPARATE DOWNLOAD

Form P1: Physiotherapist, pre-treatment

Inskrivningsformulär (ifylls av sjukgymnast/ studiesjuksköterska)

SEPARATE DOWNLOAD

Form P2: Physiotherapist, test form

NEAPE Bedömningsformulär för fysisk funktion

(sjukgymnast/studiesköterska)

preoperativt 3 mån 6 mån 12 månader

SEPARATE DOWNLOAD

Form P3: Physiotherapist or study nurse, postoperative

NEAPE uppgifter om RT och OP

Fylls i senast 3 månader efter operation.

SEPARATE DOWNLOAD

QoL formulär EQ-5D och EORTC C30 och CR29 på följande sidor

SEPARATE DOWNLOAD
